6.2 Efficacy Parameters

6.2.1 *Bladder Diary Questions*

The bladder diary will be completed daily for the 7 days prior to visit 2 and visit 6, to record the number of incontinence episodes and whether these were nocturia events. If a subject has multiple events in 1 day, each event will preferably be entered separately. The number of incontinence pads used will also be recorded in the diary.

Subjects will be instructed on how to use the bladder diary and complete the assessments.

7 STUDY CONDUCT

7.1 Observations by Visit

Visits should occur within ± 2 days of the scheduled visit. All times should be recorded using the 24-hour clock (eg, 23:20, not 11:20 PM).

7.1.1 Screening/Placebo Run-In Visit – Visit 1 (Days 0)

The following procedures are to be completed during the Screening/washout period at time points outlined on the Schedule of Assessments ([Appendix 2](#)).

- Provide informed consent and request informed consent form (ICF) signature
- Record demographic data including sex, age, race, and ethnicity
- Record medical/surgical history (including urinary and incontinence history and symptoms); record smoking history and current usage, if applicable)
- Record previous and current medications
- Measure and record vital signs (blood pressure, heart rate, and body temperature)
- Complete full physical examination (including height and weight)
- Complete the C-SSRS, BDI-II, BAI, PSQI
- Determine subject's PVR
- Draw blood for pregnancy test in women of childbearing potential
- Collect urine for dipstick test (If test is positive for nitrates and leukocyte esterase, take history of signs and symptoms of urinary tract infection and perform urine culture. If urine culture and clinical signs and symptoms are positive, the subject cannot be enrolled in the study, but can be re-screened at a later date, as long as s/he does not meet exclusion criterion 11 [chronic, or recurrent (> 4 per year) urinary tract infections]. Microscopic evaluations will be performed if the dipstick test is positive. If the dipstick test is positive at Screening, the subject must be excluded from the study.)
- Draw blood for haematology and biochemistry tests
- Perform 12-lead ECG
- Verify eligibility (inclusion/exclusion criteria)
- Dispense single-blind study drug for Placebo Run-In Period
- Dispense bladder diary and instruct subject in its use

7.1.2 Eligibility Assessment Visit – Visit 2 (Day 14)

The following procedures are to be completed during the Eligibility Assessment Visit at time points outlined on the Schedule of Assessments ([Appendix 2](#)).

- Record current medications
- Measure and record vital signs (blood pressure, heart rate, and body temperature)
- Complete full physical examination
- Complete the C-SSRS, BDI-II, BAI, PSQI
- Determine subject's PVR
- Collect urine for pregnancy test in women of childbearing potential
- Collect urine for dipstick test (If test is positive for nitrates and leukocyte esterase, take history of signs and symptoms of urinary tract infection and perform urine culture. If urine culture and clinical signs and symptoms are positive, the subject cannot be enrolled in the study, but can be re-screened at a later date, as long as s/he does not meet exclusion criterion 11 [chronic, or recurrent (> 4 per year) urinary tract infections]. Microscopic evaluations will be performed if the dipstick test is positive. If the dipstick test is positive and the microscopic evaluation is abnormal these results will be recorded as an AE with the follow-up of the AE reported to the Medical Monitor.)
- Draw blood for haematology and biochemistry tests
- Perform 12-lead ECG
- Review bladder diary
- Verify eligibility (inclusion/exclusion criteria)
- Randomise subject
- Collect single-blind study drug for Run-in Period and perform drug accountability
- Dispense double-blind study drug
- Query for AEs

7.1.3 One Week Post-randomisation Visit – Visit 3 (Day 21)

The following procedures are to be completed during the 1 Week Post-randomisation Visit at time points outlined on the Schedule of Assessments ([Appendix 2](#)).

- Record current medications
- Measure and record vital signs (blood pressure, heart rate, and body temperature)
- Complete full physical examination
- Complete the C-SSRS, BDI-II, BAI, PSQI
- Collect urine for pregnancy test in women of childbearing potential
- Draw blood for analysis of electrolytes (including sodium)

- Perform 12-lead ECG
- Collect unused study drug and perform drug accountability
- Dispense study drug
- Query for AEs, including adverse events of special psychiatric interest

7.1.4 Two Weeks Post-randomisation Visit – Visit 4 (Day 28)

The following procedures are to be completed during the 2 Weeks Post-randomisation Visit at time points outlined on the Schedule of Assessments ([Appendix 2](#)).

- Record current medications
- Measure and record vital signs (blood pressure, heart rate, and body temperature)
- Complete full physical examination
- Complete the C-SSRS, BDI-II, BAI, PSQI
- Collect urine for pregnancy test in women of childbearing potential
- Draw blood for analysis of electrolytes (including sodium)
- Perform 12-lead ECG
- Collect unused study drug and perform drug accountability
- Dispense study drug
- Query for AEs including adverse events of special psychiatric interest

7.1.5 Three Weeks Post-randomisation Visit – Visit 5 (Day 35)

The following procedures are to be completed during the 3 Weeks Post-randomisation Visit at time points outlined on the Schedule of Assessments ([Appendix 2](#)).

- Record current medications
- Measure and record vital signs (blood pressure, heart rate, and body temperature)
- Complete full physical examination
- Complete the C-SSRS, BDI-II, BAI, PSQI
- Collect urine for pregnancy test in women of childbearing potential
- Draw blood for analysis of electrolytes (including sodium)
- Perform 12-lead ECG
- Collect unused study drug and perform drug accountability
- Dispense study drug

- Query for AEs including adverse events of special psychiatric interest

7.1.6 Eight Weeks Post-randomisation/Early Termination Visit – Visit 6 (Day 70)

The following procedures are to be completed during the 8 Weeks Post-randomisation/Early Termination Visit at time points outlined on the Schedule of Assessments ([Appendix 2](#)).

If this is the Early Termination Visit, the Investigator should use every effort to encourage the subject to taper study medication for 1 week and to return for the Safety Follow-up Visit (Visit 7).

- Record current medications
- Measure and record vital signs (blood pressure, heart rate, and body temperature)
- Complete full physical examination (including weight)
- Complete the C-SSRS, BDI-II, BAI, PSQI
- Determine subject's PVR
- Collect urine for pregnancy test in women of childbearing potential if the subject is continuing in the study or collect blood for the pregnancy test if this is the ET Visit
- Draw blood for haematology and biochemistry tests
- Perform 12-lead ECG
- Collect unused study drug and perform drug accountability
- Dispense study drug for the 1-week tapering period (half of the dose to which the subject is randomized)
- Review and collect bladder diary
- Query for AEs including adverse events of special psychiatric interest

7.1.7 Post-treatment Visit/End of Study Visit – Visit 7 (Day 105)

The following procedures are to be completed during the Post-treatment Visit at time points outlined on the Schedule of Assessments ([Appendix 2](#)).

- Measure and record weight
- Record current medications
- Measure and record vital signs (blood pressure, heart rate, and body temperature)
- Complete full physical examination (including weight)
- Complete the C-SSRS, BDI-II, BAI, PSQI

- Draw blood for pregnancy test in women of childbearing potential
- Draw blood for haematology and biochemistry tests (only if abnormal values were seen at Visit 6)
- Perform 12-lead ECG (only if any abnormality seen at Visit 6 represents a clinically significant worsening from baseline)
- Collect unused study drug and perform drug accountability
- Query for AEs including adverse events of special psychiatric interest

7.2 Monitoring by telephone contact

- In addition to the visit assessments detailed above, suicide monitoring using the C-SSRS will also be performed by a telephone contact with the subject 4 weeks post randomization (study day 42).

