3 OVERALL DESIGN AND PLAN OF THE STUDY

3.1 Overview

This is a Phase 1/2a, double-blind, randomised, placebo-controlled, parallel-group study in subjects 18 to 70 years old diagnosed with UI.

The study will include a 2-week, single-blind (subject blind) Screening Placebo Run-In Period and an 8-week double-blind Treatment Period. The Treatment Period will be followed by a 1-week Dose-tapering Period. Subjects will return to the clinic for a safety Follow-up Visit 4 weeks after treatment is completed for a total study duration of 15 weeks. No interim analysis is planned.

All subjects will enter the Screening Placebo Run-In Period during which eligibility will be assessed and placebo run in medication will be provided. During this period, 7 days daily diary symptoms will be collected. Subjects who continue to meet eligibility criteria after the Screening Placebo Run-In period, including collection of diary data will enter the Treatment Period and be randomly assigned (2:1) to receive study drug (litoxetine 10 mg, 20 mg, 30mg, or placebo) BID.

[figure not shown]
Litoxetine treatment will be provided with dose titration, starting with 10 mg BID for 1 week, escalated to 20 mg BID for 1 week, and subsequently escalated to 30 mg BID for 6 weeks' duration (for a total litoxetine treatment period of 8 weeks). Placebo treatment will be matched.

If the subject does not tolerate the last dose level escalation (ie cannot tolerate 30 mg BID), the dose can be reduced to the previous dose level (20 mg BID). If the patient does not tolerate the lower dose level (20 mg BID) s/he will be discontinued from the study. After 8 weeks of treatment, doses will be reduced by 50% over 1 week to taper off treatment. A safety follow up visit will occur 4 weeks after treatment is permanently stopped (total study duration 15 weeks)

Safety assessments will be conducted throughout the trial and will include physical examinations, vital signs, evaluation of psychiatric status (suicidality, depression symptoms, anxiety and sleep related symptoms), clinical laboratory evaluations, 12-lead electrocardiograms (ECGs), and adverse events (AEs).

Efficacy will be assessed by number of urinary incontinence episodes and the number of incontinence pads used.

A schedule of assessments is provided in [Appendix 2](#). A schematic of the study design is presented in [Figure 1](#).

Figure 1: Study Design

BID = twice daily

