Appendix 2: Schedule of Assessments

Visit Number	Visit 1 ⁽¹⁾	Visit 2 ⁽¹⁾	Visit 3	Visit 4	Visit 5	Telephone contact	Visit 6	Visit 7
Visit Name	Screening/ Placebo Run In	Eligibility assessment/ Randomization (start 10 mg litoxetine or Placebo BID)	1 week Post Randomization First dose escalation (start 20 mg or Placebo BID)	2 weeks Post Randomization Second dose escalation (start 30 mg or Placebo BID)	3 weeks Post Randomization		8 weeks post Randomization Final Treatment Visit⁽⁴⁾ (ET Visit)	13 weeks post Randomization Post-Treatment Safety F/U⁽²⁾ (End of Study Visit)
Study Day	Day 0	Day 14	Day 21	Day 28	Day 35	Day 42	Day 70	Day 105
Evaluation of eligibility/randomization	X	X						
Dispensing/collection of trial drug	X	X	X	X			X ⁽¹⁴⁾	X
Patient bladder diary review/collection ⁽¹²⁾	X	X					X	
Recording of AEs		X	X	X	X		X	X

Abbreviations: AEs = adverse events; BMI = body mass index; ECG = electrocardiogram; ET = early termination; PVR = postvoid residual urine volume; UTI = urinary tract infection

- (1) Eligible subjects will undergo a 2-week Screening Placebo Run-In Period with 7 days bladder daily diary symptom collection (e-diaries). Subjects who continue to be eligible after the Screening Placebo Run-In Period will be randomised (Treatment Period).
- (2) Visit window \pm 2 days
- (3) AEs must be followed for a minimum of 30 days and until complete resolution or stabilization of the event, or as deemed appropriate by the Investigator on consultation with the Sponsor medical responsible.
- (4) If a subject is withdrawn prematurely from the trial, all procedures indicated for the Week 8 (Visit 6) visit must be performed. The Investigator should use every effort to encourage the subject to taper study medication for 1 week and to return for the Safety Follow-up Visit (Visit 7).
- (5) Serum pregnancy tests will be performed prior to entry into the trial (Visit 1), the ET Visit (Visit 6; if the subject is discontinuing the study) and at the End of Study Visit (Visit 7) for all female subjects of childbearing potential. Only those female subjects with a negative pregnancy test at Visit 1 will receive trial medication.
- (6) Urine (dipstick) pregnancy tests will be performed at Visits 2, 3, 4, 5, and 6 (if it is not the ET Visit) for all female subjects of childbearing potential. Only those female subjects with a negative pregnancy test will receive trial medication.

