2.3 Primary Endpoint(s)

Safety:

1. Incidence and severity of AEs and Adverse Events of interest (urinary retention, withdrawal symptoms) over the course of the study. AEs are recorded at visits 2,3,4,5,6 and 7.
2. Adverse Events of special psychiatry interest (nervousness, anxiety, panic attacks, insomnia, aggression, mania, suicidal ideation, development/worsening of depression) over the course of the study
3. Suicidal Adverse Events and Adverse Events suggestive of abuse potential will be analysed, and detailed narratives provided
4. Lab parameters: Haematology and chemistry recorded at visit 1,2,6 and 7. Urinalysis recorded at visit 1 and 2.
5. Absolute change from end of the Screening Placebo Run-In Period in ECG readings and Week 8 (Visit 6). ECG parameters of interest include: ventricular rate, QT interval, corrected QT interval, PR interval, and QRS duration
6. Absolute change from end of the Screening Placebo Run-In Period to each visit in standardised cuff systolic and diastolic blood pressure and radial heart rate

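### No adverse-event question is scheduled between Day 35 and Day 70, which is 35 of the 42 days at 30 mg, although subjects are telephoned on Day 42 for the C-SSRS alone

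*Protocol*

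**What the plan says.** Protocol 7.2 describes one telephone contact: "suicide monitoring using the C-SSRS will also be performed by a telephone contact with the subject 4 weeks post randomization (study day 42"). Protocol Appendix 2 and SAP Figure 1 both restrict that column to the C-SSRS. In both, the row "Recording of AEs" is blank for the call.

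SAP 2.3, item 1, matches this: "AEs are recorded at visits 2,3,4,5,6 and 7". Protocol 7.1.5 (Visit 5, Day 35) includes "Query for AEs including adverse events of special psychiatric interest", and Protocol 7.1.6 (Visit 6, Day 70) has the same instruction. Nothing between those two visits does.

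On dosing, Protocol 3.1 has treatment "subsequently escalated to 30 mg BID for 6 weeks" after one week at each lower level, and Appendix 2 starts the 30 mg step at Visit 4 (Day 28).

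AE incidence and severity is the first primary endpoint listed, and SAP 6.7 names TEAEs as the primary safety endpoint. Protocol 6.1.2.3 lets AEs come from observation, from what the subject volunteers, or from questioning; one of its sample questions looks back to the previous clinic visit.

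**The concern.** The trial's main purpose is to describe tolerability as the dose is raised. Scheduled AE questioning is weekly through 10 mg, 20 mg and the first week of 30 mg. It then stops for five weeks, the greater part of exposure at the highest dose. Appendix 2 schedules no visit in those weeks, so no vital signs, ECG or electrolytes either. The Day 42 call is the only planned contact, and it does not ask about AEs.

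Three outputs depend on how well events from this stretch are remembered:

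- the proportion of subjects with at least one TEAE, reported with Clopper-Pearson intervals (SAP 6.7);
- severity and time to onset (Protocol 8.7.2, SAP 6.8);
- the AE summaries by dose period (SAP 6.3), if they are read side by side.

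Protocol 6.1.2.3 also asks for particular attention to eight kinds of psychiatric event. The C-SSRS covers suicidality. The call asks about none of nervousness, anxiety, panic attacks, insomnia, aggression or mania.

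**Working it through.** **Inputs.** Scheduled days, from Protocol 7.1 and Appendix 2: Visit 2 = 14, "Two Weeks Post-randomisation Visit – Visit 4 (Day 28"), "Three Weeks Post-randomisation Visit – Visit 5 (Day 35"), call = 42, "Eight Weeks Post-randomisation/Early Termination Visit – Visit 6 (Day 70"), Visit 7 = 105. Visit 3 is Day 21. The visit window is ±2 days (Protocol 7.1).

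**Check of the plan's own figure.** Length of the 30 mg phase = Day 70 − Day 28 = 42 days = 6 weeks. This agrees with Protocol 3.1.

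**Intervals between scheduled AE queries** (later day minus earlier day):

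| From – to | Days | Length | Period |
|---|---|---|---|
| Visit 2 – Visit 3 | 14–21 | 7 | 10 mg |
| Visit 3 – Visit 4 | 21–28 | 7 | 20 mg |
| Visit 4 – Visit 5 | 28–35 | 7 | 30 mg, first week |
| Visit 5 – Visit 6 | 35–70 | 35 | 30 mg, remaining five weeks |
| Visit 6 – Visit 7 | 70–105 | 35 | taper and follow-up |

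**Size of the gap.**
- Share of the 30 mg phase: 35/42 = 83%.
- Share of randomised treatment (Day 70 − Day 14 = 56 days): 35/56 = 62.5%.
- Relative to the weekly interval: 35/7 = 5 times.
- With both visits at opposite ends of their windows: 35 ± 4 = 31 to 39 days.

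**With an AE question on Day 42.**
- The 30 mg intervals become 35 − 28 = 7, 42 − 35 = 7 and 70 − 42 = 28 days.
- The longest on-treatment interval falls from 35 to 28 days, from 83% to 28/42 = 67% of the phase.
- On-treatment queries after Visit 4 rise from 2 (Visits 5 and 6) to 3.
- The Day 70–105 interval is unchanged.

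**What cannot be computed.** The documents hold no figure on recall or under-reporting, so the effect on observed incidence cannot be sized.

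**The case against.** The case for leaving the schedule alone is substantial. It removes several stronger readings that a reader might draw.

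*That AEs at 30 mg go uncollected for five weeks.* They do not. Visit 6 asks about the whole interval. Volunteered events are recordable at any time up to the final follow-up visit (Protocol 6.1.2.2), including any mentioned during the Day 42 call. SAEs and AEs leading to withdrawal must be reported within 24 hours of the site learning of them (Protocol 6.1.2.1.1). Early terminators have the Visit 6 procedures when they leave. What is missing is scheduled prompting.

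*That incidence at 30 mg is understated.* This is plausible but not shown. It rests on general reasoning about recall, with nothing in the documents to quantify it.

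*That the treatment comparison is biased, or that the SAP formally compares doses under unequal recall.* SAP 6.3 evaluates differences between groups separately within each dose period, and both arms share the schedule. No test across doses is specified. The 30 mg period also includes one week with 7-day recall, and any informal reading across doses already mixes 1, 1 and 6 weeks of exposure.

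*That misremembered onset dates corrupt the by-period tables.* An event starting between Day 35 and Day 70 stays in the Visit 4 to Visit 6 period unless its onset is recalled as before Day 28. The main exposure is in the time-to-onset tabulation.

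It is also fair to say that dense contact during titration followed by sparser contact is a coherent design, that the call has a defined purpose, and that the remedy shortens the longest interval by only 7 days. What remains is that the plan gives no reason for leaving AEs out of the one contact it schedules in this interval, and the question to ask is already written in the protocol.

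**Conclusion.** The point holds as a weakness in ascertaining the primary endpoint that can be reduced cheaply. It is not an error that undermines the trial. No AE query is scheduled for 35 of the 42 days at 30 mg (31 to 39 days within the visit windows), five times the interval used at 10 and 20 mg. Mild or transient events, their severity and their onset dates may be under-ascertained over that stretch, to an unknown degree. Absolute TEAE incidence, time to onset and descriptive reading across dose periods are affected.

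This rests on two assumptions: that visits occur as scheduled, and that prompted recall over a shorter interval is at least as complete as over a longer one. The second is general knowledge and does not come from the documents.

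**What to change.** - **Protocol 7.2:** add the standard AE question of Protocol 6.1.2.3 to the Day 42 call, including the AEs of special psychiatric interest.
- **Protocol Appendix 2 and SAP Figure 1:** mark AE recording in the telephone column and lift the restriction to the C-SSRS.
- **SAP 2.3, item 1:** add the Day 42 contact to the list of times at which AEs are recorded.

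The cost is a minor amendment and a few more minutes per call, with no new contact. Protocol 7.2 does not say who makes the call, so the sponsor should confirm that the caller can record AEs. AE counts may be slightly higher.

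If the change comes mid-study, record which subjects were asked, because ascertainment will then differ between early and late subjects. If the Day 42 calls are already complete, changing the SAP cannot recover the data; the report should then state the 35-day interval beside the AE summaries.

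This fix does not touch the equal 35-day interval from Day 70 to Day 105. That interval covers the taper and follow-up, where withdrawal symptoms are a named AE of interest.

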8 STATISTICAL METHODS

8.1 General Considerations

The general objectives of this study are to establish the safety, tolerability and efficacy of litoxetine in men and women who suffer from UI. The primary analyses will focus on safety, describing the adverse events with point estimates and Clopper Pearson 95% confidence intervals. Efficacy will be explored with regards to number of incontinence episodes and will use a mixed effects model with repeated measure (MMRM). Additional statistical considerations will be addressed in the Statistical Analysis Plan (SAP).

8.2 Analysis Populations

There are 4 analysis populations for this study:

Safety population:	Defined as all subjects who are randomised, receive study drug, and undergo at least 1 visit
Intent-to-Treat (ITT) population:	Defined as all subjects who are randomized
Modified Intent-to-Treat (mITT) population:	Defined as all subjects who are randomised, receive at least 1 dose of study drug, and provide an end of study primary efficacy endpoint
Per Protocol (PP) population:	Defined as those subjects who meet the ITT criteria and have completed the study without a major protocol deviation

8.3 Disposition of Subjects

Subjects randomised and who receive study drug will be identified as completing the study or withdrawn from the study. Reasons for withdrawal will include: AE, failure to return, protocol deviation, subject request, and other.

8.4 Protocol Deviations

In addition to clinical and study conduct protocol deviations, subjects that fail to provide valid measurements **of the bladder diary** at the end of the Placebo Run-In Period and at the end of the Treatment Period will be considered protocol deviations. Additionally, subjects that do not meet compliance criteria will be considered protocol deviations.

8.5 Demographics, Baseline Characteristics, and Concomitant Medications

Demographics, baseline characteristics (including smoking history and current usage, if applicable), medical history, and concomitant medications will be reported for the subjects in the study.

